## 6. RISKS ASSOCIATED WITH PROCEDURES

### 6.1 Risk Summary

This protocol is modestly invasive with only one (1) IV catheter for blood sampling, therefore overall risk appears modest for IV catheter and mild for OGTT and MRI.

### 6.2 Detailed Risks

#### 6.2.1. Fasting, and Caffeine, NSAID and Exercise Restriction

Risks include:

- feelings of hunger
- irritability
- fatigue
- light-headedness
- dizziness

There are no risks of NSAID restriction if NSAIDs are not prescribed by a physician for clinical care. There are no risks of acute abstention from exercise. These risks are considered minimal. See Letters of Support from physicians who regularly require fasting procedures in pediatric populations (section [11. Supplemental Information](#)).

#### 6.2.2. Maximal Exercise Test

Risks include:

- Feelings of exertion, fatigue, and breathlessness
- Discomfort due to VO2 monitoring equipment (i.e. mouthpiece or mask)
- Serious complications including orthopedic injury, myocardial infarction, arrhythmia, hemodynamic instability, and death are rare (Takken 2016; van Brussel 2019)

These risks are considered minimal, resolving quickly (seconds to minutes) after test termination. See Letters of Support from pediatric physicians who regularly perform maximal exercise testing in pediatric populations (section [11. Supplemental Information](#)).

#### 6.2.3. Intravenous Catheter and Venipuncture

Risks include:

- bruise or clot formation
- infection
- pain at the site of catheter insertion/venipuncture
- hematoma after withdrawal
- soreness over the site

These should all be transient and resolve after several days.

#### 6.2.4. Blood sampling

Risks include:

- Pain at site of blood draw
- Bleeding
- Infection
- Dizziness

Poses no further risk than IV catheterization.

#### 6.2.5. OGTT

Risks include:

- Nausea
- Vomiting
- Abdominal bloating
- Headache
- Hypoglycemia

These risks are uncommon or rare.

#### 6.2.6. MRI

MRI uses a powerful magnetic field, not ionizing radiation, to create an image of the scanned area of the body. No contrast agent will be used.

Risks include:

- There are no known risks of MRI, aside from the standard risks associated with persons with certain metallic implants. If potential participants have a metallic implant, cardiac pacemaker, or are pregnant, they will be disqualified.
- Sensation of claustrophobia or anxiety, particularly in individuals susceptible to it.
- People with metallic implants, such as prostheses or aneurysm clips, or persons with electronic implants, such as cardiac pacemakers, the magnetic field generated by the magnetic resonance machine can cause a displacement or malfunctioning of these devices.
- We know of no risks or adverse effects from the radio signals used in this study.
- Some people have also reported tingling or tapping sensations, or muscle twitches in different parts of their body during the imaging procedure.
  - These sensations are not hazardous and should not cause discomfort to the participants.
- A small increase in risk may be associated with rapid gradient waveform switching times associated with fast MR imaging. In certain situations, the rapid switching of gradient waveforms has caused peripheral nerve stimulation in subjects.
  - Significant nerve stimulation, however, has not occurred as long as the imaging system has been programmed to stay within certain limitations of gradient strength and switching time (dB/dt).
- Occasionally, people who have clasped their hands tightly together during the study have reported a feeling of electrical shock in their hands and arms.

- This is also not hazardous; however, to avoid any possible discomfort, participants will be instructed to not clasp their hands together during the study.
- Women who are pregnant must not participate in this study. The potential risks to a fetus from the MRI scan are not definitely known.
- The MR scanner produces loud tapping sounds during operation, which may reach somewhat objectionable levels.
- Anatomical abnormalities
  - Images will not be reviewed by neuroradiology
  - Any obvious abnormalities will be reported to the IRB upon discovery for assistance in determining how to proceed with potential reporting

All MR scanners currently used at the University of Wisconsin stay within these guidelines and have received FDA approval for use in humans. All pulse sequences used in this study are designed to stay within the current guidelines for dB/dt established by the FDA.

#### **6.2.7. Subject Monitoring**

An automatic blood pressure cuff around the upper arm may feel uncomfortable while inflated, but this is temporary (30-60 seconds). Blood pressure measures are considered very safe.

#### **6.2.8. Cognitive Testing**

Sensitive information may be collected during the cognitive testing visit during the structured parental interview assessing the child's quality of life. The one measure with questions that may indicate illegal behaviors and suicidal ideation is the Child Behavior Checklist (CBCL).

The following items on the CBCL are notable:

- Item 2: drinks alcohol without parental approval
- Item 18: Deliberately harms self or attempts suicide
- Item 28: breaks rules at home, school, or elsewhere
- Item 57: physically attacks people
- Item 59: plays with sex parts in public
- Item 82: steals outside of the home
- Item 91: talks about killing self
- Item 99: smokes, chews, or sniffs tobacco
- Item 101: truancy, skips school
- Item 105: uses drugs for nonmedical purposes
- Item 106: vandalism

The answers to these questions may indicate illegal behaviors or psychiatric distress (e.g. suicidal ideation) which may be socially stigmatizing. Answers to sensitive questions will be safeguarded (see section [7.9.4 Protecting the Confidentiality of Participant Data](#)).

#### **6.2.9. DEXA Scan**

The x-ray exposure during this test is very small (~30% of a typical chest X-ray) and is well below the levels that result in a high risk of harmful effects. The radiation dose for a whole-body scan is approximately 7 microSieverts. Using a background radiation dose of 2.4 mSv, this equates to a BERT value of about 24 hours (1 day).

## 7. DATA AND SAFETY MONITORING PLAN

### 7.1. Monitoring study safety

The study team and PI will monitor study data and safety through two different mechanisms:

1. During study visits, trained [name] lab staff will be present to address any immediate safety concerns. [name] lab staff will document all expected and unanticipated problems as described in this protocol.
2. We will complete internal audits of all subject files on a quarterly basis (see section [7.8 Internal Audits](#)). These internal audits will identify any unanticipated outcomes or trends, and [name] lab staff can then notify the IRB and the DMC of any new, common, or unanticipated adverse events.

The PI and the research team will consult if there are subject complaints or an adverse event is experienced (anticipated or unanticipated). The PI and the research team will review the data to ensure the subject populations are safely handling the study conditions and experimental conditions, that all procedures are being followed per IRB approved protocol, and that all forms are completed to ensure compliance with IRB regulations. Further, study staff will discuss concerns or subject safety issues, including the potential need to modify study procedures to reduce risk.

In addition to the monitoring of the study by the PI and study team, the PI has contracted with the Institute for Clinical and Translational Research Data Monitoring Committee (ICTR DMC) to provide independent, ongoing data and safety monitoring.

### 7.2. Data Monitoring Committee (DMC)

The ICTR DMC provides investigators with independent services to ensure appropriate measures are in place to promote subject safety, research integrity and compliance with federal regulations and local policies for individual clinical research protocols in need of DMC review as determined by the PI, the funding agency, the local Scientific Review Committee, or the local IRB, and for which no DMC exists. For these studies, the UW ICTR DMC will be the primary data and safety advisory group for the PI.

The DMC is supported in its mission of safety and compliance by experienced ICTR staff to provide administrative assistance, experienced members representing a diversity of backgrounds, skills and knowledge, and the use of REDCap which allows more efficient tracking of protocols and protocol subjects. In providing oversight for the conduct of this study, the ICTR DMC will meet on a biannual basis throughout the study. Additional meetings may be scheduled as determined by the DMC or as requested by the PI. The DMC members will review protocol-specific reports created by statisticians that serve a non-voting member role on the DMC using data pulled from the REDCap. These standard reports will include an overview of study objectives, a review of actual and projected accrual rates, an evaluation of patient demographics for balance of randomization (if applicable), and a summary of the number and seriousness of adverse events. An interim analysis of study results may be performed and source documents may be reviewed to allow the DMC to independently judge whether the overall integrity and conduct of the protocol remain acceptable based on data provided and reported by the PI. The DMC will make recommendations to the PI that could include actions of continuation, modification, suspension, or termination.

Data Type	Frequency of Review	Reviewers
Subject accrual (including compliance with protocol enrollment criteria)	Every 6 months	ICTR Data Monitoring Committee, PI
Subject demographics	Every 6 months	ICTR Data Monitoring Committee, PI
Status of all enrolled subjects as of date of reporting	Every 6 months	ICTR Data Monitoring Committee, PI
Primary outcome analysis	Every 6 months	ICTR Data Monitoring Committee
AEs and rates	Every 6 months	ICTR Data Monitoring Committee, PI
SAEs	Per occurrence	ICTR Data Monitoring Committee, PI

### 7.3. Adverse Event (AE) Reporting

This study will utilize the Common Terminology Criteria for Adverse Events (CTCAE) v5.0 for adverse event monitoring and reporting. This information can be downloaded from the CTEP home page ([http://ctep.info.nih.gov/CTC4/ctc\\_ind\\_term.htm](http://ctep.info.nih.gov/CTC4/ctc_ind_term.htm)).

The severity of the event will be graded using the CTCAE. In addition, for comparison to the CTCAE, adverse events will be tabulated using a 3-level schema as defined below:

- Mild
  - Event may be noticeable to patient
  - Does not influence daily activities
  - Usually does not require intervention.
- Moderate
  - Event may be of sufficient severity to make patient uncomfortable
  - Performance of daily activities may be influenced
  - Intervention may be needed.
- Severe
  - Event may cause severe discomfort
  - Usually interferes with daily activities; patient may not be able to continue in the study
  - Treatment or other intervention usually needed.

Note the distinction between the severity and the seriousness of an AE. A severe event is not necessarily an SAE. For example, a headache may be severe (i.e. interferes significantly with patient's usual function) but would not be classified as serious unless it met one of the criteria for SAEs.

Next, it will be determined by the PI and study physician or clinical neuropsychologists whether the event is expected or unexpected and if the AE is related to the intervention or study procedures. With this information, it will be determined whether an AE should be reported as an expedited report in addition to submission via routine clinical data.

Expedited AE reporting may require e-mail notification, phone, or fax submission of a written report as directed below. All expedited AE reports will be submitted to the IRB of record, the UW Health Sciences Institutional Review Board (HS IRB) in the case of this study.

### 7.3.1. Assessment of Attribution

Attribution of AEs will be assessed in relation to the study procedures. When assessing whether an adverse event is related to a study procedure, the following attribution categories are utilized:

- Definitely Related
  - An AE categorized as definite is clearly related to study procedures. If the timing of the AE is definitely consistent with the exposure to the study related procedures and it is most likely that the AE was caused by the study procedures such as because a high occurrence of the AE was expected based on the study intervention materials. In this case, the PI may categorize the AE as definitely related.
- Probably Related
  - An AE that is likely related to study procedures. If the timing of the AE is consistent with the exposure to the study intervention and it is more likely that the AE was caused by the study procedures than not, the PI may categorize the AE as Probable.
- Possibly Related
  - An AE that may be related to study procedure. If the timing of the AE is reasonably consistent with the exposure to the study intervention, and there is another cause of the AE that could be equally likely, the PI may categorize the AE as Possible.
- Unlikely Related
  - An Unlikely AE is one that is doubtfully related to study procedures. The coincidence of the AE with the exposure of the investigational product or intervention should be assessed. An AE that continued while the intervention was interrupted or stopped, or if the AE resolved while the intervention continued, may be categorized as Unlikely. If there is another more likely cause of the AE, the PI may determine that the AE was unlikely related to the study intervention.
- Not Related/Unrelated
  - An Unrelated AE is one that is clearly NOT related to study procedures. An AE may be considered Unrelated if the subject did not receive the study intervention or if there is another obvious cause of the AE (for example, a car accident or other disease/condition).

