#### **4.3.4.j. Intravenous Catheter**

Only during MRI-OGTT visit. An IV catheter will be placed by trained personnel in the antecubital fossa or hand using standard aseptic technique. Study staff trained and delegated in phlebotomy/IV placement, WIMR staff, research nurse, or higher study-associated clinical authority (e.g. physician) will insert an IV using standard medical procedures. The IV catheter will remain in place for approximately 2 hours.

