### 7.10.2 Subject Stopping Guidelines

Each intervention (i.e. study visit) will be terminated based on the following specific guidelines:

- If the subject wishes to stop
- If the subject complains of serious pain or discomfort
- If the subject is admitted to hospital for psychiatric distress
- If the subject complains of (related to MRI):
  - Discomfort
  - Anxiety
  - Claustrophobia
- If baseline glucose is  $\geq 126$  mg/dL and is not the result of non-compliance with fasting requirement (see [4.1.2. Exclusion Criteria](#))
- Any SAE occurring during study procedures

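### The Unlikely Related category in 7.3.1 keeps a stop-the-treatment (dechallenge) criterion that does not fit brief procedures, and the section leaves study intervention undefined

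*Combined protocol and SAP*

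**What the plan says.** Section 7.3.1 opens with a clear frame: "Attribution of AEs will be assessed in relation to the study procedures". The category definitions then use other terms. Unlikely Related starts from a doubtful relation to study procedures, asks about exposure to an investigational product or intervention, and adds: "An AE that continued while the intervention was interrupted or stopped, or if the AE resolved while the intervention continued, may be categorized as Unlikely". It closes by allowing the category where another cause is more likely. Unrelated starts from a clear absence of relation to study procedures and adds: "An AE may be considered Unrelated if the subject did not receive the study intervention". Section 7.3.1 does not define the intervention. The only gloss is in the subject stopping guidelines (7.10.2): "Each intervention (i.e. study visit) will be terminated based on the following specific guidelines".

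On durations, 4.3.4.j states: "The IV catheter will remain in place for approximately 2 hours". Section 6.2.3 lists five catheter and venipuncture harms (bruise or clot, infection, site pain, hematoma after withdrawal, soreness) and says of them: "These should all be transient and resolve after several days".

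Section 7.3 says that expectedness and relatedness are settled first, and then: "With this information, it will be determined whether an AE should be reported as an expedited report".

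**The concern.** A dechallenge criterion makes sense when exposure continues. If the harm persists after the treatment is withdrawn, or clears while it goes on, the treatment is a less likely cause. A needle stick, a short-term catheter, a glucose drink or an exercise test gives no such information. An injury from a brief procedure normally lasts beyond it, so the criterion counts the expected course of a caused harm as a reason to doubt causation.

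The undefined term raises a second question. If study intervention means something narrower than study procedures, an assessor could think that an event after a screening procedure came before any intervention. Venipuncture is done only at screening (4.3.4.i). The exercise test and DEXA are done there by default, although 4.3.2.b lets them move to other visits.

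At stake is whether related events are recorded as related in an adolescent study, and whether that judgment then steers an event away from an expedited report.

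**Working it through.** The plan gives no figure to reproduce. The check sets the criterion beside the durations that the protocol states.

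**Step 1: length of exposure.**
- Venipuncture (4.3.4.i): a single needle stick.
- IV catheter (4.3.4.j): about 2 hours.
- OGTT (4.3.4.h): a drink taken within 5 minutes, with blood sampling for 60 minutes.
- Maximal exercise test (4.3.4.e): about 8-12 minutes on average.

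**Step 2: expected course of the harms, and which half of the criterion they fit.**
- Catheter and venipuncture (6.2.3): several days for all five. If several days means at least two (an assumption), that is 2 × 24 = 48 hours against about 2 hours. Result: 5 of 5 are expected to be present after the procedure has ended, and so fit the first half (continues after stopping) on a literal reading. The hematoma appears only after withdrawal, so it persists after stopping, though whether it continued can be argued.
- Exercise symptoms (6.2.2): expected to clear seconds to minutes after the test ends. They also fit the first half.
- OGTT harms (6.2.5, five listed): no duration is given, so the answer depends on what counts as exposure. If it is the 5-minute drink, harms that outlast it fit the first half. If it is the whole visit of about 2 hours, those that clear within the visit fit the second half (resolves while the intervention continues).
- Cuff discomfort (6.2.7): present only during inflation, 30-60 seconds. It ends with the exposure and fits neither half.

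**Step 3: overlap with Probably Related.** That category needs timing consistent with exposure and a procedure that is, on balance, the likelier cause. A bruise at the catheter site meets both conditions. The same bruise also fits the dechallenge sentence. Both categories are worded permissively, and 7.3.1 has no rule of precedence between them.

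**Step 4: does the intervention include screening?**
- Pointing to no: 7.10.2 equates intervention with study visit, and screening (4.3.2) is described apart from Study Visits (4.3.3).
- Pointing to yes: the table of study visits in 4.3.5 has the screening visit as its first column. The total in 4.5 for completing all study visits is reached only with screening included: 60 + 60 + 30 + 60 = $210 at the low end and 60 + 90 + 30 + 60 = $240 at the high end. The lead sentence of 7.3.1 speaks of procedures, and the SAE definition in 7.4 names the screening phase.

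Usage is mixed, so the term is ambiguous.

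**Step 5: what attribution affects.**
- It is an input to the expedited-report decision (7.3). Section 7.6 sets expedited timelines only for SAEs and does not say which SAEs fall under which timeline.
- It does not affect recording: all AEs go into REDCap (7.5).
- It does not affect SAE review: the PI, study physician, DMC and IRB review every SAE (7.5), and the DMC sees SAEs per occurrence (7.2).

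**The case against.** The strongest reply is that each category is governed by its opening test. A catheter-site hematoma is not doubtfully related to a procedure, so a sensible assessor would choose Probably Related. The dechallenge sentence only says what may be done, and normal completion of a procedure is arguably not an interruption or a stop. Much of this stands: nothing obliges anyone to misclassify an event. It does not remove the defect, because the higher categories are equally permissive, and because a visit ended early under 7.10.2 meets the stopping condition squarely while the bruise from its catheter still persists.

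A reader might infer more than the documents support:
- *Virtually every AE can be called Unlikely.* No. Some harms end with the exposure, and the sentence sits under the test of doubtful relation.
- *Harms of a screening exercise test count as Unrelated by rule.* No. That requires carrying the 7.10.2 gloss into 7.3.1 and reading study visit as excluding screening, against 4.3.5, 4.5, 7.4 and the lead sentence of 7.3.1.
- *Grave harms could go unreviewed.* Section 6.2.2 does say "Serious complications including orthopedic injury, myocardial infarction, arrhythmia, hemodynamic instability, and death are rare", but such events meeting the SAE definition reach the PI, study physician, DMC and IRB whatever their attribution.
- *The Definitely Related category shuts out rare harms.* Its reference to an expected high occurrence is only an example.
- *The deciders conflict.* Section 7.3 names the PI with the study physician or neuropsychologists. The mention of the PI in 7.3.1 is compatible with that.

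**Conclusion.** The point holds as a drafting defect of modest size. A stated attribution criterion does not fit the study's procedures. On the protocol's own durations, 5 of 5 listed catheter and venipuncture harms can literally be placed in Unlikely while also meeting a higher category. Exercise symptoms fit the criterion as well, and OGTT harms may, depending on how exposure is read. The status of screening procedures under the term study intervention is unclear, but it is not settled against them.

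The likely effect is under-attribution of mainly non-serious procedural events, with some influence on the expedited-report decision in 7.3. Recording of AEs and review of SAEs are unaffected. The plan specifies no count of related events for the DMC (7.2 lists the number and seriousness of AEs, and rates), so no planned analysis is biased. For the same reason, routine DMC reports would not necessarily reveal under-attribution.

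The conclusion assumes that the end of a procedure can be read as stopping and that the text is applied literally. How often assessors would do so cannot be estimated from the documents.

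**What to change.** In 7.3.1:
1. Delete the dechallenge sentence from Unlikely Related.
2. Base that category on an onset whose timing is implausible relative to the procedure, or on a more likely alternative cause. The second ground is already there.
3. Replace study intervention, intervention and investigational product throughout with *any study procedure, including screening procedures*. The condition under Unrelated then becomes that the subject had undergone no such procedure before onset.

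Removing the sentence also removes the overlap with Probably Related that it creates, so no separate precedence rule is needed for it.

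The cost is a few sentences and a matching edit to the AE form, with no new data or staff. The number of AEs classed as related may rise slightly.
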